7.5. Safety Assessments

Safety evaluations will be conducted as described below. Refer to [Table 1](#), [Table 2](#), and [Table 3](#) for the timing of all safety assessments.

7.5.1. Clinical Safety Assessments

7.5.1.1. Weight and Height

Height (without shoes) in centimeters (cm) and weight (indoor clothing without shoes) in kilograms (kg) will be measured.

7.5.1.2. Physical Examination, Vital Signs, and ECOG Performance Status

Physical examination must be performed for Parts A and B as indicated in [Table 1](#), [Table 2](#), and [Table 3](#) and for Part C as indicated in [Table 5](#), [Table 6](#), and [Table 7](#).

These examinations will be performed according to the standards at each institution. The physical examination will be performed on the scheduled day, even if study treatment is being withheld. More frequent examinations may be performed at the discretion of the investigator and if medically indicated. If baseline/screening examinations are performed within 3 calendar days prior to the first dose of study treatment, they need not be repeated on C1D1 (except vital signs, which must be conducted on C1D1).

Complete physical examinations should include general appearance, skin, neck, eyes, ears, nose, throat, lungs, heart, abdomen, back, lymph nodes, extremities, and neurological examinations.

Symptom-directed physical examinations should include body systems as appropriate. These examinations will be performed according to the standards at each institution.

Information about the physical examinations must be present in the source documentation at the study site. The results of the physical examination prior to the start of study dosing must be included on the Medical History eCRF. Clinically relevant findings made after the start of study dosing, which meet the definition of an AE, must be recorded on the AE eCRF.

Vital signs include systolic and diastolic BP, pulse measurements, and body temperature (°C or °F). Vital signs should be assessed pre-dose on the scheduled visit day, if possible. BP and pulse rate should be measured after the patient has been in a supine or sitting position for 5 minutes. BP should be assessed on the same arm throughout the study.

ECOG performance status assessments ([Oken 1982](#)) will be performed during the study to assess how the disease affects the daily living abilities of the patients ([Appendix 1](#)).

7.5.1.3. Echocardiography and Electrocardiography

An echocardiogram or multiple gated acquisition (MUGA) scan to assess cardiac function and risk of cardiac dysfunction, including cardiomyopathy is required at Screening (Day -30 to Day -1) and at the EoT Visit. Additional echocardiogram or MUGA scans may be performed

throughout the study if clinically indicated at the discretion of the Investigator. The same procedure (either MUGA or echocardiogram) should be performed at screening/baseline and subsequent visits. Preferably the same cardiologist/radiologist should read and report the outcome to minimize variability in results. Copies of all transthoracic echocardiograms and/or MUGA scans performed on subjects who experience a greater than or equal to 20% decrease in left ventricular ejection fraction (LVEF) from baseline and whose cardiac ejection fraction is below the institution's lower limit of the normal range (LLN) will be required by Karyopharm for review.

A single standard 12-lead ECG will be performed for patients in Part A and B. Patients must rest for at least 5 minutes prior to the ECG recording. The Investigator will interpret the ECG using one of the following categories: normal, abnormal but not clinically significant, or abnormal and clinically significant. The date and time the ECG is performed and the following parameters will be recorded in the eCRF: heart rate, PR interval, QT interval, QRS interval, and QT corrected using Bazett's formula.

7.5.1.4. Ophthalmic Examination

For Parts A and B, an ophthalmic examination by an optometrist or ophthalmologist is required at Screening and the EoT Visit, and if clinically indicated (at the discretion of the Investigator) during the study (e.g., monitoring of pre-existing cataracts, visual disturbances).

Patient reporting *de novo* or worsening of visual symptoms should immediately be referred for further examination.

The ophthalmic examination is to include the following:

- Prior to dilation:
 - best corrected visual acuity
 - slit lamp examination (for cataracts or other abnormalities)
 - tonometry
- Following dilation:
 - fundoscopy
 - slit lamp examination to document lens clarity

If a cataract/lens opacity is seen during the examination, the cataract/lens opacity will be graded according to a Grade 1-4 system.

An ophthalmic examination is not required for patients enrolled in Part C, but may be performed at any time during the study if clinically indicated (at the discretion of the Investigator).

7.5.1.5. Concomitant Medications

Concomitant medications will be documented for each patient at each scheduled visit during the treatment phase. A detailed history of medications will be documented during Screening and C1D1. Subsequently, at each study visit, patients will be asked whether they have taken any medication other than the study treatment (from Screening through the EoT Visit). All

concomitant medications including dietary supplements, over-the-counter medications, and oral herbal preparations, as well as changes in medication, will be recorded on the eCRFs.

Necessary supportive care such as appetite stimulants, anti-emetics, and anti-diarrheals, etc., are allowed (see [Table 16](#) and Section [6.9.1](#)).

7.5.2. Rheumatology Consultation and Testing

At the Investigator's discretion, in consultation with the Karyopharm Medical Monitor, a rheumatological consultation is recommended for patients with clinically significant joint or muscle-related AEs. Rheumatology testing is recommended as clinically indicated and may be completed as clinically indicated per institutional standards (e.g., antinuclear antibodies, rheumatoid factor, C-reactive protein, erythrocyte sedimentation rate, uric acid [if not already available], or other autoantibodies based on symptoms).

7.5.3. Hematology Consultation, Testing, and Biopsy

At the Investigator's discretion (after the screening assessment), in consultation with the Karyopharm Medical Monitor, a hematology consultation is recommended for patients with clinically significant hematological AEs, including any grade of treatment-emergent anemia or abnormal reticulocyte counts. Hematological testing (including but not limited to standard hematological evaluations and erythropoietin level) ± bone marrow biopsy may be performed as clinically indicated per institutional standards. In addition, assessments for vitamin B12, folate, iron, erythropoietin, haptoglobin, and transferrin levels and reticulocyte counts will be completed as described in Section [7.5.4.2](#).

7.5.3.1. Adverse Events

Information regarding AEs and SAEs will be collected. See Section [8](#).

It is the responsibility of the Investigator to record and document all SAEs (occurring from the signing of the informed consent form [ICF]) and all AEs (occurring from the first dose of study treatment on C1D1) throughout the study and for 30 days after the last dose of study treatment.

Each AE will be graded according to the CTCAE v4.03 at every visit (Section [8.1.3](#)).

7.5.4. Laboratory Safety Assessments

7.5.4.1. Clinical Laboratory Tests

[Table 19](#) presents the clinical laboratory tests that will be performed during the study.

Table 19: Clinical Laboratory Tests (Parts A, B, and C Unless Indicated)

Complete Blood Count with Differential (Blood sample: whole blood; ethylenediaminetetraacetic acid) tests including)				
Hemoglobin	Hematocrit	Mean corpuscular volume	Mean corpuscular hemoglobin	Mean corpuscular hemoglobin concentration
WBC count	WBC differential ¹ (Parts A and B Only)	RBC count	Lymphocytes	Monocytes
Neutrophils	Band neutrophils (Parts A and B Only)	Eosinophils	Basophils	Platelets
Reticulocyte count				
Complete Serum Chemistry (Blood sample: serum)				
Sodium	Potassium	Chloride	Bicarbonate	Blood urea nitrogen
Creatinine	Glucose	Calcium	Phosphate	Magnesium
ALT	AST	Alkaline Phosphatase	Total bilirubin ²	Lactate dehydrogenase
Total protein	Albumin	Amylase ³	Lipase ³	Creatinine kinase
Urate	Thyroid-stimulating hormone ³			
Coagulation				
Prothrombin time (Parts A and B Only)	International normalization ratio (Parts A and B Only)	Activated thromboplastin time (Parts A and B Only)		
Urinalysis ⁴				
Appearance (Parts A and B Only)	Color (Parts A and B Only)	Urine bilirubin (Parts A and B Only)	Glucose (Parts A and B Only)	Hemoglobin (Parts A and B Only)
Ketones (Parts A and B Only)	pH (Parts A and B Only)	Protein (Parts A and B Only)	Specific gravity (Parts A and B Only)	Urobilinogen (Parts A and B Only)

Abbreviations: ALT = alanine aminotransferase; AST = aspartate aminotransferase; RBC = red blood cell; ULN: upper limit of normal; WBC = white blood cell.

- ¹ WBC differential may be automated or manual as per institutional standards. Blasts should be included.
- ² If the total bilirubin concentration is increased $> 1.5 \times$ ULN, total bilirubin should be differentiated into the direct and indirect reacting bilirubin.
- ³ If not included in the complete serum chemistry panel at the site, amylase, lipase, and TSH must be performed at the time points indicated in [Table 1](#), [Table 2](#), and [Table 3](#) for Parts A and B and [Table 5](#), [Table 6](#), and [Table 7](#) for Part C.

⁴ Microscopy will only be performed if clinically indicated at the discretion of the Investigator. Urinalysis is only required for Parts A and B.

All laboratory safety assessments will be performed and analyzed at each site by a certified local laboratory. The Investigator or designee will review the laboratory results and assess the clinical significance of all abnormal values. Appropriate action will be taken for any clinically significant abnormal values. Values will be documented on the laboratory report until stabilized, or the laboratory value returns to a clinically acceptable range (regardless of relationship to study treatment) or baseline.

In addition, laboratory safety assessments will be collected and analyzed on the scheduled day, even if study treatment is being withheld. More frequent assessments may be performed if clinically indicated, or at the Investigator's discretion and these should be recorded on the Unscheduled Visit eCRFs.

Any laboratory value that remains abnormal at the EoT Visit and that is considered clinically meaningful will be followed according to accepted medical standards for up to 30 days or until resolution of the abnormality or return to baseline. Toxicity will be graded using CTCAE Version 4.03.

Karyopharm must be provided with a copy of the laboratory certification and normal ranges for each parameter measured. In addition, if at any time a patient has laboratory parameters obtained from a different outside laboratory, Karyopharm must be provided with a copy of the certification and normal ranges for that laboratory.

7.5.4.2. Vitamin B12, Folate, Iron, Erythropoietin, Haptoglobin, and Transferrin Levels and Reticulocyte Counts

Vitamin B12, folate, iron, erythropoietin, haptoglobin, and transferrin levels and reticulocyte counts will be assessed at Screening and the EoT Visit. Additionally, patients with treatment-emergent anemia should have these analyte levels/counts assessed as soon as possible after onset. Patients with \leq Grade 1 anemia should have their levels/counts assessed no less than once a month from and patients with \geq Grade 2 anemia should have their levels/counts assessed every 2 weeks from onset. A hematology consultation is recommended as appropriate (see Section 7.5.3). Supportive care recommendations for deficiencies in these analytes are noted in Section 6.9.1.

7.5.4.3. Pregnancy Testing

For females of childbearing potential, a negative serum human chorionic gonadotropin (hCG) pregnancy test must be obtained < 3 days prior to Cycle 1 Day 1 and at the EoT Visit. Test sensitivity for hCG must be ≥ 25 mIU/mL. Pregnancy testing is to be performed as clinically indicated at the discretion of the Investigator during the study.

7.6. Other Assessments

7.6.1. Collection of Information on Antineoplastic Therapy

Information on any antineoplastic therapies used after discontinuation of study treatment will be collected.

8. SAFETY DEFINITIONS, RECORDING, AND REPORTING

Note: For urgent medical issues in which the Karyopharm Medical Monitor should be contacted, please refer to the *Study Manual* for complete contact information.

8.1. Adverse Events

8.1.1. Definitions

- *Adverse event (AE)*: Any untoward medical occurrence in a patient or clinical investigation subject administered a pharmaceutical product and which does not necessarily have to have a causal relationship with this treatment. An AE can therefore be any unfavorable and unintended sign (including an abnormal laboratory finding, for example), symptom, or disease temporally associated with the use of study treatment, whether or not considered related to the study treatment.
- *Treatment-emergent adverse event (TEAE)*: Any event that was not present prior to the initiation of study treatment or any event already present that worsens in either intensity or frequency following exposure to study treatment.
- *Serious adverse event (SAE)*: Any untoward medical occurrence that, at any dose, results in death; is life threatening (i.e., an event in which the patient was at risk of death at the time of the event; it does not refer to an event that hypothetically might have caused death if it were more severe); requires inpatient hospitalization or prolongation of existing hospitalization; results in persistent or significant disability/incapacity; or is a congenital anomaly/birth defect. (See Section 8.2.2 for additional information about SAE reporting.)

8.1.2. Recording of Adverse Events

Adverse Events will be reported and recorded in the eCRF from the time of the first dose of study drug through 30 days after the last dose of study drug or until the start of subsequent antineoplastic therapy, whichever occurs first. That is, if a patient begins a new antineoplastic therapy, the AE reporting period for nonserious AEs ends at the time the new treatment is started.

Adverse events (including laboratory abnormalities that constitute AEs) should be described using a diagnosis whenever possible, rather than individual underlying signs and symptoms. When a clear diagnosis cannot be identified, each sign or symptom should be recorded as a separate AE.

The Investigator should ask the patient non-leading questions to determine if any AEs have occurred during the study, since the last study visit. Adverse events may also be recorded when they are volunteered by the patient, or through physical examination, laboratory tests, or other clinical assessments.

An AE should be followed, and an assessment should be made at each visit (or more frequently, if necessary) for any changes in severity of the event, the suspected relationship to the study treatment, the interventions required to treat the event, and the outcome.

All AEs occurring during the study are to be followed up in accordance with good medical practice until they are resolved, stabilized or judged no longer clinically significant or, if a chronic condition, until fully characterized.

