8.2.1. Recording of Serious Adverse Events

It is the responsibility of the Investigator to record and document all SAEs occurring from the signing of the ICF until at least 30 days after the patient has stopped study treatment. All SAEs must be reported on an SAE report form, in addition to being recorded in the eCRF. The original SAE report form must be retained in the Investigator’s site file.

All applicable sections of the form must be completed in order to provide a clinically thorough report. The Investigator must assess and record the relationship of each SAE to study treatment and complete the SAE Report Form (in English).

See ICH E2A (Clinical Safety Data Management: Definitions and Standards for Expedited Reporting, Attachment 1) for key data elements that are required for expedited reporting.

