8.2.2. Reporting of Serious Adverse Events

Every SAE, regardless of the causal relationship to the study treatment, occurring after the patient has signed informed consent, until at least 30 days after the patient has stopped study treatment, must be reported to the Karyopharm Pharmacovigilance Department within *24 hours* of learning of its occurrence. The investigational site personnel must use the SAE Report Form provided by Karyopharm for reporting any SAE to the Karyopharm Pharmacovigilance Department.

Upon completion, the SAE Report Form must be immediately emailed or faxed to:

Pharmacovigilance Department
Karyopharm Therapeutics Inc.
Email: [contact]
[contact] (USA)

Any SAE observed after the 30-day follow-up period should only be reported to Karyopharm if the Investigator suspects that the SAE has a causal relationship to study treatment. Recurrent episodes, complications, or progression of the initial SAE must be reported as follow-up to the original episode within 24 hours of the Investigator receiving the follow-up information.

An SAE should be followed until its resolution or until it is judged to be permanent, and assessment should be made at each visit (or more frequently, if necessary) of any changes in severity of the event, the suspected relationship to the study treatment, the interventions required to treat the event, and the outcome.

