9.8.1. Adverse Events

Adverse Events (AEs) will be coded using the MedDRA dictionary and displayed in tables and listings using System/Organ/Class (SOC) and Preferred Term. Analyses of AEs will be performed for those events that are considered to be treatment-emergent AEs (TEAEs), defined as any AE with onset or worsening of a pre-existing condition on or after the first administration of study medication through 30 days following last dose or any event considered drug-related by the Investigator through the end of the study. Adverse events with partial dates will be assessed using the available date information to determine if treatment-emergent; AEs with completely missing dates will be assumed to be treatment-emergent.

Adverse events will be summarized by frequency counts at patient level. Tabulations will be provided for all TEAEs, for TEAEs assessed by the Investigator as at least possibly related to treatment, for \geq Grade 3 TEAEs, and for serious AEs (SAEs).

No formal hypothesis-testing analysis of AE incidence rates will be performed.

All AEs (treatment-emergent and post-treatment) will be listed in patient data listings. Separate by-patient listings will be provided for the following: patient deaths, SAEs, and AEs leading to withdrawal.

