# 5.1.1. Definitions of Treatment-Emergent Adverse Events (TEAEs), Serious Adverse Events (SAEs), and Treatment-Emergent Treatment-Related Adverse Events (TRAEs)

# **5.1.1.1.** Treatment-Emergent Adverse Event (TEAE)

• Treatment-emergent adverse events (TEAE) of study treatment are defined as any event that was not present prior to the initiation of study treatment (KPT-9274 and/or niacin

and/or nivolumab) or any event already present that worsens in either intensity or frequency following exposure to study treatment, from the first dose of study treatment to 30 days after the last dose of study treatment inclusive, or the day before the start of a new antineoplastic treatment, whichever occurs first. Additionally, any AEs that occurred 30 days after the last dose of study treatment or after the start of a new antineoplastic treatment will also be considered as TEAE, if assessed by the Investigator as related to any drug of the study treatment.

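### Protocol 7.5.3.1, 8.1.2 and 9.8.1 and SAP 2.4/5.1.1.1 set different AE windows, so late non-serious related AEs count as treatment-emergent but have no matching collection rule

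*Protocol*

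**What the plan says.** Four places define when an AE is recorded or counted.

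- **Protocol 8.1.2 (recording).** AEs are recorded from the first dose "through 30 days after the last dose of study drug or until the start of subsequent antineoplastic therapy, whichever occurs first". The next sentence gives the scope of the stop: once a patient begins another anticancer treatment, "the AE reporting period for nonserious AEs ends at the time the new treatment is started".
- **Protocol 7.5.3.1 (recording).** The investigator records all AEs from the first dose "throughout the study and for 30 days after the last dose of study treatment". New therapy is not mentioned.
- **Protocol 9.8.1 (analysis).** Treatment-emergent AEs (TEAEs) are those with onset or worsening from the first dose "through 30 days following last dose or any event considered drug-related by the Investigator through the end of the study". There is no cut at new therapy.
- **SAP 5.1.1.1 (analysis).** The base window runs to 30 days after the last dose "or the day before the start of a new antineoplastic treatment, whichever occurs first". AEs occurring 30 days after the last dose "or after the start of a new antineoplastic treatment will also be considered as TEAE", provided the investigator judges them related. This extension is not restricted to serious events. SAP 2.4 ends the treatment period with the same new-therapy cut.

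Serious events have separate rules. Section 8.2.1 requires recording of "all SAEs occurring from the signing of the ICF until at least 30 days after the patient has stopped study treatment". Section 8.2.2 adds: "Any SAE observed after the 30-day follow-up period should only be reported to Karyopharm if the Investigator suspects" a causal link to study treatment.

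Section 9 of the protocol says that changes to its analyses will be described in the SAP. SAP 1.7 declares none.

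**The concern.** A site cannot follow both 7.5.3.1 and 8.1.2 for a patient who starts another anticancer therapy within 30 days of the last dose. Whether a non-serious AE reaches the database then depends on which section the site read. Separately, both TEAE definitions extend to related events that the recording rules leave out.

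A primary endpoint is touched. The synopsis makes Grade 3 or higher AEs part of the primary safety endpoints for Parts A, B and C, and 8.1.2.1 says that a Grade 3 or 4 event is not automatically serious. The SAE rules therefore do not capture every such event.

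**Working it through.** The plan gives no figure to reproduce, so the check sets the rules side by side by type of event. Day 30 means 30 days after the last dose.

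| Event (time of onset) | Recorded, 8.1.2 | Recorded, 7.5.3.1 | TEAE, 9.8.1 | TEAE, SAP 5.1.1.1 |
|---|---|---|---|---|
| 1. Non-serious, before new therapy, by day 30 | yes | yes | yes | yes |
| 2. Non-serious, unrelated, after new therapy, by day 30 | no | yes | yes | no |
| 3. Non-serious, related, after new therapy, by day 30 | no | yes | yes | yes |
| 4. Non-serious, related, after day 30 | no | no | yes | yes |

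**Serious events.** SAEs are recorded to at least 30 days after treatment stops (8.2.1), and later ones are reported if suspected to be related (8.2.2). New therapy does not end either rule, so there is no collection gap.

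**Row 2** is a conflict of definitions: the protocol counts the event and the SAP does not. An unrelated SAE in that interval is classified in the same two ways, but it is at least collected, and SAP 5.1.4 lists all SAEs.

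**Row 3** is a collection gap at any site that follows 8.1.2.

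**Row 4** is a collection gap under both recording sections. Aligning 8.1.2 with 7.5.3.1 would close row 3 but not row 4. The 3-monthly contacts do not close it as designed: Tables 3 and 7 have no AE mark in the follow-up column, and the call footnotes (19 for Parts A and B, 13 for Part C) ask about survival, disease status, general condition and new therapies.

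**Size.** The documents give neither the share of patients who start new therapy within 30 days nor the rate of late related events. On assumed values only, for row 3:

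patients with a missed event = planned enrolment × share starting new therapy by day 30 × share of those with a new related non-serious AE afterwards

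- Low: 175 × 0.10 × 0.05 = 0.9, about 1 patient (0.5%).
- High: 175 × 0.50 × 0.20 = 17.5, about 18 patients (10%).

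Only the 175 comes from the documents. The width of the range shows that the effect cannot be pinned down. Row 4 comes on top, again at an unknown rate.

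**The case against.** The strongest counter-argument has four parts.

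1. **The SAP and 8.1.2 largely agree.** The SAP base window and SAP 2.4 use the same new-therapy cut as 8.1.2. A reader might infer that the TEAE set as a whole cannot be filled. The documents do not support that: only the related-AE extension reaches beyond collection, and related SAEs do populate it. This stands and narrows the point.
2. **Section 7.5.3.1 refers the reader to Section 8,** so 8.1.2 can be taken as the governing rule. That softens the conflict between the two recording sections. It does not resolve the mismatch with 9.8.1 or with the SAP extension.
3. **Stopping non-serious collection at new therapy is defensible,** because attribution becomes confounded. True, but the analysis definition should then stop there too.
4. **Little of the primary endpoint is exposed.** DLTs are confined to the first 28 days of treatment, and AEs leading to discontinuation precede any new therapy. AEs already recorded are followed until resolved or stable, and SAP 5.1.2 counts repeated occurrences of an event once per patient. This stands and limits the likely effect.

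A reader might also infer a loss from the share of the 30-day window cut off. If 30% to 60% of patients started new therapy on day 14, it would be 0.3 × 16/30 = 16% to 0.6 × 16/30 = 32%. Those inputs have no source in the documents. For Parts A and B, eligibility requires that standard options considered useful are exhausted, so a quick move to another therapy cannot be taken for granted. The figure also measures observation time for all AEs, whereas the SAP excludes unrelated AEs after new therapy by design.

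**Conclusion.** The windows conflict in current text, and following 8.1.2 leaves two kinds of non-serious related AE uncollected although they are TEAEs by definition: those after new therapy and those after day 30. In addition, unrelated AEs after new therapy but within 30 days are TEAEs under 9.8.1 and not under the SAP, a departure that SAP 1.7 does not declare.

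The direction of any bias is downward for late non-serious related toxicity, including non-serious Grade 3 or higher events. The size cannot be computed from the documents; the 1 to 18 patients above are an illustration on assumed rates.

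A reader might infer that AE collection as a whole stops at new therapy, or that toxicity is in fact undercounted. Neither follows. SAEs remain covered by 8.2.1 and 8.2.2, and an undercount is possible but not shown.

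**What to change.** Reconcile protocol 7.5.3.1, 8.1.2 and 9.8.1 with SAP 2.4 and 5.1.1.1, so that one collection window supports one TEAE definition.

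- **To day 30.** Preferably record all AEs to 30 days after the last dose whether or not new therapy has started, and apply any new-therapy cut in the analysis. The 30-day safety call already asks about AEs and collects information on new anticancer therapy; its start date must be recorded so that the cut can be applied.
- **After day 30.** Either limit the related-AE extension in 9.8.1 and SAP 5.1.1.1 to what is collected, that is related SAEs, or add collection of related non-serious AEs.
- **SAP 1.7.** State whatever departure from protocol 9.8.1 remains.

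The cost is wording in the protocol and SAP and a few more AE entries up to day 30. Collecting non-serious related AEs at the 3-monthly contacts would be a new task, because AEs are not scheduled there; limiting the extension avoids it. An amendment works forward only. Section 1.2.1 reports 47 patients treated by 2 March 2019, so the study report should say which recording rule applied to patients already treated.
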